9.6.4.3. Secondary Efficacy Analysis

The change from baseline in weekly average of the daily worst PI-NRS over the past 24 hours up to week 16 and the baseline FIQR score will be analyzed in the same manner as the primary efficacy endpoint; however, the baseline pain intensity over the past 24 hours and the baseline FIQR score, respectively, will be used as a covariate in the MMRM model instead of the baseline PI-NRS score.

The PGIC asks patients to rate their status on the following scale:

Since the start of the study, my overall status is:
1. Very Much Improved
2. Much Improved
3. Minimally Improved
4. No Change
5. Minimally Worse
6. Much Worse
7. Very Much Worse

The PGIC data will be dichotomized, where a patient who responds as either “much improved” or “very much improved” will be considered improved, and all other responses will be considered not improved. The response variable will be analyzed using a logistic regression model with the treatment, age group at FM onset, and sex as explanatory factors. In addition, the PGIC data will be summarized as categorical variable by week and treatment group using descriptive statistics.

The percentage of patients who experience $\geq 30\%$ reduction and $\geq 50\%$ reduction in the weekly average of the daily average PI-NRS score up to week 16 will be analyzed using a generalized estimating equation method, where the dependent variable experience $\geq 30\%$ reduction and $\geq 50\%$ reduction (Yes/No) will be modeled through the binomial link function, with treatment, sex, age group at FM onset, week, and treatment by week interaction as explanatory factors. In addition, a plot of percentage of improvement versus percentage of patients meeting the improvement level throughout the study will be presented by treatment group.

Change from baseline up to week 16 in the PROMIS Sleep Disturbance SF8a score, change from baseline up to week 16 in the PROMIS Physical Function SF12a score, change from baseline up to week 16 in PROMIS Fatigue SF8a score, and change from baseline up to week 16 in the HADS will be analyzed using an MMRM model with treatment, sex, age group at FM onset, week, treatment-by-week interaction, and baseline value of the corresponding variable as explanatory factors.

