
The PGIC data will be dichotomized, where a patient who responds as either “much improved” or “very much improved” will be considered improved, and all other responses will be considered not improved. The response variable will be analyzed using a generalized estimating equation (GEE) method logistic regression model with the logit link function, with treatment, sex, age group at FM onset, month, and treatment by month interaction sex as explanatory factors. In addition, the PGIC data will be summarized as categorical variable by month week and treatment group using descriptive statistics. Data collected from patients after discontinuing treatment will be excluded and considered missing for this analysis.
 
...
 
Change from baseline in the PROMIS Sleep Disturbance SF8a score will be analyzed using the same MMRM model as the primary efficacy endpoint with baseline Sleep Disturbance SF8a score as a covariate.
 
Change from baseline in the PROMIS Physical Function SF12a score, change from baseline in PROMIS Fatigue SF8a score, and change from baseline in the HADS will be analyzed using an MMRM model with treatment, sex, age group
	
The PGIC data will be dichotomized, where a patient who responds as either “much improved” or “very much improved” will be considered improved, and all other responses will be considered not improved. The response variable will be analyzed using a logistic regression model with the treatment, age group at FM onset, and sex as explanatory factors. In addition, the PGIC data will be summarized as categorical variable by week and treatment group using descriptive statistics.
 
...
 
Change from baseline in the PROMIS Sleep Disturbance SF8a score, change from baseline in the PROMIS Physical Function SF12a score, change from baseline in PROMIS Fatigue SF8a score, and change from baseline in the HADS will be analyzed using an MMRM model with treatment, sex, age group at FM onset, week, treatment-by-week interaction, and baseline value of the corresponding variable as explanatory factors.
 
The number and percentage of patients who did not complete the treatment due to lack of efficacy or adverse event will be summarized using descriptive statistics, and the time to treatment discontinuation due to lack of efficacy or adverse event will be analyzed using the
	
This change was made to correct the analysis for secondary efficacy endpoints.

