This Statistical Analysis Plan (SAP) describes the planned analysis and reporting for Teva Branded Pharmaceutical Products R&D, Inc. study TV48125-PN-20028, (A Multicenter, Randomized, Double-Blind, Placebo-Controlled, Proof of Concept Study of the Efficacy and Safety of Fremanezumab for Treatment of Patients with Fibromyalgia), and was written in accordance with SOP GBP_RD_702 (Statistical Analysis Plan).

The reader of this SAP is encouraged to read the study protocol for details on the conduct of this study, the operational aspects of clinical assessments, and the timing for completing the participation of a patient in this study.

The SAP is intended to be in agreement with the protocol, especially with regards to the primary and all secondary endpoints and their respective analyses. However, the SAP may contain more details regarding these particular points of interest, or other types of analyses (e.g. other endpoints). When differences exist in descriptions or explanations provided in the study protocol and this SAP, the SAP prevails; the differences will be explained in the Clinical Study Report (CSR).

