The change from baseline in FIQR symptom sub-score, impact sub-score, functional sub-score, and total score will be analyzed, respectively, using a MMRM method with change from baseline in the FIQR score at weeks 4, 8, and 12 as the dependent variable, sex, age group at FM onset, week, treatment, and treatment by week interaction as fixed factors, and the baseline FIQR score as a covariate. ARH(1) for repeated observations within patients will be used, and the denominator degrees of freedom will be estimated using Kenward-Roger's approximation. Missing total score will be considered as missing at random.

Notes, if ARH(1) does not converge, then simpler covariance structures with less parameters will be used in the following order until the model converges: AR[1]; CSH; and CS.

The LS mean estimates for the mean change from baseline as well as the difference of the estimates between the fremanezumab and placebo group, with the corresponding SE, p-value and associated 95% CI will be provided. The results from all visits will be presented.

SAS codes are:

```
ODS OUTPUT LSMEANS= LS DIFFS = DIFF (WHERE = (AVISIT = _AVISIT));  
PROC MIXED DATA= name;
```

```
CLASS SUBJID TRT01PN AVISIT AGEATFMONSET SEX;
```

Statistical Analysis Plan

```
MODEL CHANGE= BASE TRT01PN AGEATFMONSET SEX AVISIT  
TRT01PN*AVISIT/DDFM=KR;  
REPEATED AVISIT/SUBJECT= SUBJID TYPE= ARH(1);  
LSMEANS TRT01PN*AVISIT / DIFF CL;  
RUN;  
ODS OUTPUT CLOSE;
```

Where AVISIT denotes the study visit/week; BASE denotes the baseline value for the FIQR scores.

In addition, the FIOR scores will be summarized using descriptive statistics for all visits.

6.3.2. The Patient Global Impression of Change Rating at Week 12

The PGIC scale evaluates all aspects of patients' health and assesses if there has been an improvement or decline in clinical status since the start of the study. Patients will record responses to the PGIC scale visits 6 and 7 (weeks 12 and 16). Improvement is recorded on a 7-point scale, with 1 indicating very much improved, 4 indicating no change, and 7 indicating very much worse:

- 1 = Very Much Improved
- 2 = Much Improved
- 3 = Minimally Improved
- 4 = No Change
- 5 = Minimally Worse
- 6 = Much Worse
- 7 = Very Much Worse

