For analysis purpose, a dichotomous scale of 'Yes' or 'No' will be derived. Scale "much improved" or "very much improved" will be considered improved (Yes), and all other non-missing responses will be considered not improved (No). Missing category will be presented as appropriate.

The response variable (yes or no) at week 12 will be analyzed using a logistic regression model with the treatment, age group at FM onset, and sex as explanatory factors. Missing category will not be included.

SAS code is:

```
ods output diffs = dif LSMeans = ls;  
PROC GENMOD DATA =name;  
CLASS TRT01PN STRATAR SEX;  
MODEL AVALCAT1 = TRT01PN STRATAR SEX / DIST=BIN TYPE3;  
LSMEANS trt01pn/exp DIFF CL;  
RUN;  
ods output close;
```

Statistical Analysis Plan

```
data ls;
set ls;
** p = estimated response rate;
p = logistic(estimate);
p_l = logistic(Lower);
p_u = logistic(Upper);
run;
```

Where AVALCAT1 denotes the responses with ‘yes’ for improved and ‘no’ for not improved.

In addition, the PGIC data will be summarized as a categorical variable using descriptive statistics for all visits, including missing category as appropriate.

6.3.3. Percentage of Patients Who Experience a $\geq 30\%$ or $\geq 50\%$ Reduction in the Weekly Average of the Daily Average PI-NRS Score at Week 12

The weekly average of the daily average PI-NRS score with missing data imputation from the 500 imputed data sets derived as described in steps 1 to 3 of Section 6.2.2 will be used to calculate the pain intensity reduction (%) from baseline in the weekly average of the daily average PI-NRS score using formula [2].

$$\frac{\text{baseline value} - \text{postbaseline value}}{\text{baseline value}} \times 100\% \quad [2]$$

The percentage of patients who experience $\geq 30\%$ reduction and $\geq 50\%$ reduction in the weekly average of the daily average PI-NRS score at week 12 will be analyzed using a generalized estimating equation (GEE) method where the dependent variable is $\geq 30\%$ reduction (Yes/No) or $\geq 50\%$ reduction (Yes/No), respectively, [REDACTED]

SAS code for GEE model:

```
ods output LSMeans = ls;
PROC GENMOD DATA =name;
  BY _IMPUTATION_;
  CLASS SUBJID TRT01PN WEEK STRATAR SEX;
  MODEL AVALCAT = BASE TRT01PN WEEK STRATAR SEX
          TRT01PN*WEEK/ DIST=BIN TYPE3;
  REPEATED SUBJECT = SUBJID / TYPE = AR(1);
  LSMEANS trt01pn*week/exp DIFF CL;
RUN;
ods output close;
```

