Where AVALCAT denotes the responses with ‘yes’ for $\geq 30\%$ or $\geq 50\%$ or ‘no’ for $< 30\%$ or $< 50\%$ pain intensity reduction, respectively.

The 500 sets of results from above analyses will be combined using Rubin’s formulae (PROC MIANALYZE).

```
PROC SORT DATA= LS;
```

Statistical Analysis Plan

```

    BY WEEK TRT01PN _IMPUTATION_ ;
RUN;

ODS OUTPUT PARAMETERESTIMATES= LSM_O;
PROC MIANALYZE DATA= LS;
    BY WEEK TRT01PN;
    MODELEFFECTS ESTIMATE;
    STDERR STDERR;
RUN;

DATA LSM_O;
    SET LSM_O;
    EXPESTIMATE = EXP(ESTIMATE);
    P = 100*EXPESTIMATE/(1 + EXPESTIMATE);
    P_LL = 100*EXP(LCLMEAN)/(1 + EXP(LCLMEAN));
    P_UL = 100*EXP(UCLMEAN)/(1 + EXP(UCLMEAN));
RUN;

```

In addition, the mean percentage of reduction and its associated 95% CI will be reported by week.

A plot of percentage of improvement versus percentage of patients meeting the improvement level at week 12 will be presented based on observed data and missing data at week 12 will be deemed as pain intensity increased from baseline. The x-axis representing percentage of improvement will be from ≥ 0 to 100% by an increment of 10%, ie., the x-axis will be at cutoff points $\geq 0\%$, $\geq 10\%$, $\geq 20\%$, ..., $\geq 90\%$ and 100% while y-axis will be percent of patients meet the cutoff points. The percentage of improvement will be calculated using formula [2].

6.3.4. Change From Baseline to Week 12 in the Weekly Average of the Daily Worst PI-NRS Score Over the Past 24 Hours

The weekly average of the daily worst PI-NRS score over the past 24 hours will be analyzed in a manner analogous to the primary endpoint as described in Section 6.2.2. The dependent variable is the change from baseline in the weekly average of the daily worst PI-NRS scores. The covariate will be baseline average of the daily worst PI-NRS scores.

6.3.5. Change From Baseline to Week 12 in the Patient-Reported Outcomes Measurement Information System Sleep Disturbance Short Form 8a Score

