The PROMIS sleep disturbance Short Form 8a (SF8a) scale contains 8 items and assesses sleep disturbance over the past 7 days. One item assessing overall sleep quality use a scale of *very poor, poor, fair, good, or very good*. Other 7 items use a scale of *not at all, a little bit, somewhat, quite a bit, or very much*. Each item of the PROMIS sleep disturbance SF8a is on 5-point scales (1 to 5), with 1 for the lowest sleep disturbance and 5 for the highest sleep disturbance. The total score ranges from 8 to 40 (highest sleep disturbance). Collection of the PROMIS sleep disturbance SF8a will start the day of the BAPS Visit (Visit 2) and will be administered weekly via the e-diary. The total raw score ranging from 8 to 40 (highest sleep disturbance) will be calculated as the summation of 8 non-missing scores. If any of 8 items has a missing score, the total raw score will be missing. The calculated total raw score will be converted into t-score

using the scoring table ([PROMIS-Sleep Disturbance Scoring Manual](#)). All questions must be answered in order to produce a valid score using the scoring table. The analysis will be based on t-score.

The change from baseline to week 12 in t-score of the PROMIS sleep disturbance SF8a will be analyzed using MMRM method in manner analogous to the analysis as described in Section 6.3.1. The dependent variable is the change from baseline in the t-score of the PROMIS sleep disturbance SF8a at analysis weeks 1 to 12 (12 levels). BASE is the t-score of the PROMIS sleep disturbance SF8a at baseline. Missing will be considered as missing at random. The results from all visits will be presented using descriptive statistics.

Summary statistics will include data from all analysis weeks.

6.3.6. Change from Baseline to Week 12 in the Patient-Reported Outcomes Measurement Information System Physical Function SF12a Score

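### In the SAP, the PGIC responder model is the only visible week-12 efficacy regression with no baseline term; adding baseline pain would be a cheap, minor improvement

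*Protocol*

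**What the plan says.** PGIC response (much or very much improved) at week 12 is a secondary endpoint. The sentence that sets its model stands in current Protocol 9.6.4.3 and in the synopsis: "The response variable will be analyzed using a logistic regression model with the treatment, age group at FM onset, and sex as explanatory factors". SAP 6.3.2 says the same in text, and its code reads "MODEL AVALCAT1 = TRT01PN STRATAR SEX / DIST=BIN TYPE3". Neither has a baseline term.

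The other unredacted week-12 efficacy regressions in the SAP all have one:

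- Primary endpoint (6.2.2): baseline average PI-NRS.
- FIQR scores (6.3.1): "and the baseline FIQR score as a covariate".
- Daily worst pain (6.3.4): "The covariate will be baseline average of the daily worst PI-NRS scores".
- PROMIS sleep (6.3.5): "BASE is the t-score of the PROMIS sleep disturbance SF8a at baseline". PROMIS physical function (6.3.6) and fatigue (6.3.7) follow the same pattern.
- 30% and 50% pain responders (6.3.3): the code has "MODEL AVALCAT = BASE TRT01PN WEEK STRATAR SEX". The SAP sentence naming the factors is blacked out, so the code is the only evidence.

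Discontinuation for lack of efficacy (6.3.8) is Kaplan-Meier only, with no regression. SAP 6.4 is redacted and is not counted.

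The protocol differs on one of these. Its pain-responder GEE (9.6.4.3) is specified "with treatment, sex, age group at FM onset, week, and treatment by week interaction as explanatory factors", with no baseline. The SAP Introduction settles which document governs: "the SAP prevails; the differences will be explained in the Clinical Study Report (CSR".

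**The concern.** PGIC is rated only at weeks 12 and 16, so it has no baseline to adjust for. That explains the omission but does not require it. The 14-day baseline mean of the daily average PI-NRS is defined in SAP 4.2 and used in the primary model, and Protocol 4.1 (criterion e) requires at least 12 of 14 diary days for entry. Randomization is stratified by sex and age at onset (Protocol 5.9, SAP 2.2), not by pain. So neither the design nor the PGIC model deals with a chance difference between arms in baseline pain.

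If baseline pain predicts who reports being much improved, two things follow. The PGIC odds ratio moves with whatever imbalance occurs, and some power is given up. The pain-responder results reported beside it would be baseline-adjusted and the PGIC result would not.

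**Working it through.** **Inputs from the documents.** 80 patients per arm (Protocol 9.2, SAP 2.4). The study ended for futility after the second interim analysis (SAP 2.5.1), and the final number per arm is not given. The documents give no PGIC response rate, odds ratio, or association with baseline pain.

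**Assumed inputs.** Placebo response 30%; conditional odds ratio 1 or 2.5; log-odds of response per SD of baseline pain, g, of 0, 0.2, 0.5 or 0.8 in size; 80 per arm, and 50 per arm to reflect the early stop.

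**The plan's own figure.** The only precision statement concerns the primary endpoint: with SD 2.2 and 80 per arm, at least 90% probability that the 95% CI half length is below 0.74. The half length is t(0.975, 158) × s × sqrt(2/80), where 158 × s²/2.2² is chi-square on 158 df. This gives 91.8%, so the statement reproduces. It says nothing about PGIC and supplies only the 80 per arm used below.

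**Chance imbalance.** The standardized difference in mean baseline pain between two arms of 80 has standard deviation sqrt(2/80) = 0.158. Its 95% limit is 1.96 × 0.158 = 0.31 SD.

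**Effect on the unadjusted odds ratio.** To first order, an imbalance d multiplies it by exp(g × d), upward or downward according to sign:

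| g | d = 0.158 | d = 0.31 |
|---|---|---|
| 0 | 1.00 | 1.00 |
| 0.2 | 1.03 | 1.06 |
| 0.5 | 1.08 | 1.17 |
| 0.8 | 1.13 | 1.28 |

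Simulation supports this (4000 trials per setting; logistic models with treatment, sex and age group, with and without baseline pain). At odds ratio 1 and 80 per arm, the unadjusted log odds ratio changes by 0.22, 0.52 and 0.70 per SD of imbalance for g = 0.2, 0.5 and 0.8. With baseline pain in the model the corresponding values are 0.01, 0.02 and 0.05, so adjustment removes the dependence. Since 0.70 is below 0.8, the formula is slightly high at the top: exp(0.698 × 0.31) = 1.24, and 1.28 is an upper end. At 50 per arm the 95% limit is 1.96 × sqrt(2/50) = 0.39 SD, and exp(g × d) runs from 1.08 (g = 0.2) to 1.37 (g = 0.8).

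**Standard error and power, without → with baseline pain.**

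| g | SE of log OR (OR 1, 80 per arm) | Power (OR 2.5, 80 per arm) | Power (OR 2.5, 50 per arm) |
|---|---|---|---|
| 0 | 0.353 → 0.356 | 79.4% → 79.5% | 59.8% → 59.7% |
| 0.2 | 0.354 → 0.358 | 80.1% → 80.2% | 58.6% → 58.5% |
| 0.5 | 0.353 → 0.365 | 76.1% → 78.1% | 55.3% → 57.6% |
| 0.8 | 0.353 → 0.379 | 69.9% → 75.0% | 50.7% → 55.0% |

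The standard error rises, yet power does not fall beyond simulation error, because the conditional odds ratio lies further from 1. At g = 0.8, odds ratio 2.5 and 80 per arm, the mean log odds ratio goes from 0.831 to 0.953 and its standard error from 0.339 to 0.368, so the ratio rises from 2.45 to 2.59.

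**Type I error of the planned model.** 4.4% to 5.3% over all settings with odds ratio 1.

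**The case against.** The case for leaving the model alone is respectable. PGIC already asks about change since the start of the study, so omitting another instrument's baseline is a defensible prespecified choice, and both stratification factors are in the model. The pain-responder comparison is imperfect, because there baseline is the denominator of the response itself. PGIC is one of several secondary endpoints in a proof-of-concept study with no multiplicity adjustment (SAP 7) that has already stopped for futility. The shift is also small against sampling error: a standard error of 0.353 puts the 95% limits a factor of exp(1.96 × 0.353) = 2.0 either side of the odds ratio. All of this stands, and it keeps the point minor. None of it shows that omitting baseline pain is better.

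Four stronger readings are tempting, and the documents and the calculation do not support them:

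- *Precision is thrown away.* For a logistic odds ratio the standard error rises on adjustment. What may be lost is power.
- *Baseline imbalance passes in full into the odds ratio, or biases it.* It enters only in proportion to an association the documents do not give, is nil if that association is nil, and leaves type I error intact.
- *PGIC is the exception in both documents.* It is so in the SAP. The protocol's pain-responder GEE lists no baseline either.
- *Amendment 03 removed a baseline term.* The superseded PGIC model shown in Protocol 16.5 had none.

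**Conclusion.** The point holds as a minor improvement. In the governing SAP, PGIC response is the only unredacted week-12 efficacy regression without a baseline term, although a suitable covariate is already collected. Over an assumed association of 0.2 to 0.8 log-odds per SD, the omission exposes the odds ratio to a shift of about 1.06 to 1.28 at the 95% limit of imbalance with 80 per arm (1.03 to 1.13 for an imbalance of one standard deviation, 0.158) and costs about 0 to 5 points of power. These sizes rest wholly on the assumed association, the 30% placebo rate and the planned arm size. No conclusion of the trial is shown to depend on it.

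**What to change.** In SAP 6.3.2 and Protocol 9.6.4.3 (with the matching synopsis sentence), add the baseline average of the daily average PI-NRS as a continuous covariate: `MODEL AVALCAT1 = BASE TRT01PN STRATAR SEX`. Define BASE there explicitly, because the SAP uses that name for different variables in different models. Make the same change in the per-protocol repeat (SAP 6.1). SAP 2.5.2 allows for amendments approved before database lock, with the randomization codes still blinded; the change should be made within that limit.

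The cost is one degree of freedom and no new data. There is a small downside to report. The odds ratio becomes conditional on baseline pain, with a standard error on the log scale about 1% to 7% larger at odds ratio 1 and up to about 9% larger at 2.5. The back-transformed response rates in SAP 6.3.2 are then rates at mean baseline pain.

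SAP Section 18 lists no changes from the protocol. It should record this one if only the SAP is amended, and also the baseline term already in the pain-responder code.

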16.6. Amendment 02 Dated 16 April 2019

The primary reasons for this amendment are to describe the method and timing of the collection of e-diary assessments, to reflect the change in the assessment scale used to evaluate concurrent conditions, and to correct errors surrounding the timing of visits during the screening period. This amendment is considered to be substantial (ie, requires approval by a CA, IEC, and/or IRB) by the sponsor’s Authorized Representative. Other nonsubstantial changes have been made to the protocol (and protocol synopsis, as appropriate). These changes are unlikely to affect the safety or rights (physical or mental integrity) of the patients in this clinical study or the scientific value of the clinical study.

Table 1 (Study Procedures and Assessments) and Figure 1 (Overall Study Schematic Diagram) have been revised to reflect changes described below.

Original text with changes shown	New wording	Reason/Justification for change
Section 1.1 Introduction (Other sections affected by this change: Sections 3.3, 3.5, 4.1)		

According to the 2010/2014 2016 American College of Rheumatology FM diagnostic criteria (Wolfe et al 2016), FM may be diagnosed when all of the following criteria are met:
 
1. There is a widespread pain index (WPI) \geq7 and a symptom severity (SS) scale score \geq5 or WPI of 3 to 6 and SS score \geq9.
 
2. Symptoms have been present at a similar level for at least 3 months.
 
3. The patient does not have a disorder that would otherwise explain the pain.
 
1. Generalized pain, defined as pain in at least 4 of 5 regions, is present.
 
2. Symptoms have been present at a similar level for at least 3 months.
 
3. Widespread pain index (WPI) \geq7 and symptom severity (SS) scale score \geq5 OR WPI of 4 to 6 and SS scale score \geq9.
 
4. A diagnosis of FM is valid irrespective of other diagnoses. A diagnosis of FM does not exclude the presence of other clinically
	
According to the 2016 American College of Rheumatology FM diagnostic criteria (Wolfe et al 2016), FM may be diagnosed when all of the following criteria are met:
 
1. Generalized pain, defined as pain in at least 4 of 5 regions, is present.
 
2. Symptoms have been present at a similar level for at least 3 months.
 
3. Widespread pain index (WPI) \geq7 and symptom severity (SS) scale score \geq5 OR WPI of 4 to 6 and SS scale score \geq9.
 
4. A diagnosis of FM is valid irrespective of other diagnoses. A diagnosis of FM does not exclude the presence of other clinically important illnesses.
	
This change was made to ensure FM diagnosis is made using current diagnostic criteria.

Original text with changes shown	New wording	Reason/Justification for change
important illnesses.		
[REDACTED]	[REDACTED]	[REDACTED]
[REDACTED]	[REDACTED]	[REDACTED]
Section 3.1 General Study Design and Study Schematic Diagram		
The study duration will be from March May 2019 until approximately March May 2021.	The study duration will be from May 2019 until approximately May 2021.	This change was made to reflect the shift in study start and completion date.
Section 3.2 Planned Number of Patients and Countries		
The study is planned to be conducted in the United States of America in approximately 25 30 investigational centers.	The study is planned to be conducted in the United States of America in approximately 30 investigational centers.	This change was made to accommodate shifts in the program timeline.
Section 3.6 e-Diary and Tablet Data Collection (Other sections affected by this change: Sections 3.5, 4.1, 4.3, Appendix A, Appendix B)		

e-Diary and Tablet Data Collection
 
The primary data collection tools that will be used in this study are the e-diary and the tablet administered by Stefanini (Appendix A).
 
e-Diary
 
The e-diary will be dispensed to each patient at the BAPS Visit (Visit 2). The e-diary will be used to record the following data:
 
 • Average PI-NRS rating • Worst PI-NRS rating • At-the-moment PI-NRS rating • Rescue medication use • Amount of rescue medication used for a specific breakthrough pain episode • Time of rescue medication used for a specific breakthrough pain episode • PROMIS Sleep Scale (Morning Report only) 	
e-Diary and Tablet Data Collection
 
The primary data collection tools that will be used in this study are the e-diary and the tablet administered by Stefanini (Appendix A).
 
e-Diary
 
The e-diary will be dispensed to each patient at the BAPS Visit (Visit 2). The e-diary will be used to record the following data:
 
 • Average PI-NRS rating • Worst PI-NRS rating • At-the-moment PI-NRS rating • Rescue medication use • Amount of rescue medication used for a specific breakthrough pain episode • Time of rescue medication used for a specific 	
This change was made to specify the method and timing of collection of electronic assessments throughout the study.

Original text with changes shown	New wording	Reason/Justification for change

The e-diary will be completed per the Study Procedures and Assessments (Table 1). The e-diary will contain the following reports, which will guide the patient through completion of the necessary data collection on any respective day during the study: Evening Report, Make-up Evening Report, Morning Report, and Make-up Morning Report. The Evening Report will be available to patients each evening for completion between 1800h and 2200h. The Evening Report will have audible alarms that will sound at 3 different times before the entry window expires or upon completion of the report. If a patient cannot complete or forgets to complete the Evening Report, a Make-up Evening Report will become available for completion between 0300h and 1300h the next day. The Make-up Evening Report will also have audible alarms that will sound 3 times during this interval but will cease to sound upon completion of the report.
 
The Morning Report will be available to patients for completion between 0300h and 1300h on the respective day as scheduled in Table 1. The Morning Report will have audible alarms that will sound at 3 different times during this interval but will cease to sound upon completion of the report. If a patient cannot complete or forgets to complete the Morning Report, a Make-up Morning Report will become available for completion between 1800h and 2200h the same day. The Make-up Morning Report will not have separate audible alarms because it becomes available during the same time interval as the Evening Report for that day, which does have audible alarms.
 
The Rescue Medication tab will be available to patients 24 hours per day; tapping this tab will automatically display all required information for the patient to complete. The e-diary main menu will have tabs for each of the aforementioned reports, on which the patient will tap to access the respective report. In the case of a missed report, the respective report will have “Missed” as an indicator to the patient on the main menu. Patients will be trained by the site staff on the use of the e-diary at Visits 1 and 2, and at each visit throughout the study. Additional information on the e-diary can be found in the Study Manual.
 
Tablet
 
The tablet will be dispensed to each clinical site. Patients will use the tablet at their visits to complete the required assessments. The tablet
	
breakthrough pain episode
 
 PROMIS Sleep Scale (Morning Report only) 
The e-diary will be completed per the Study Procedures and Assessments (Table 1). The e-diary will contain the following reports, which will guide the patient through completion of the necessary data collection on any respective day during the study: Evening Report, Make-up Evening Report, Morning Report, and Make-up Morning Report. The Evening Report will be available to patients each evening for completion between 1800h and 2200h. The Evening Report will have audible alarms that will sound at 3 different times before the entry window expires or upon completion of the report. If a patient cannot complete or forgets to complete the Evening Report, a Make-up Evening Report will become available for completion between 0300h and 1300h the next day. The Make-up Evening Report will also have audible alarms that will sound 3 times during this interval but will cease to sound upon completion of the report.
 
The Morning Report will be available to patients for completion between 0300h and 1300h on the respective day as scheduled in Table 1. The Morning Report will have audible alarms that will sound at 3 different times during this interval but will cease to sound upon completion of the report. If a patient cannot complete or forgets to complete the Morning Report, a Make-up Morning Report will become available for completion between 1800h and 2200h the same day. The Make-up Morning Report will not have separate audible alarms because it becomes available during the same time interval as the Evening Report for that day, which does have audible alarms.
 
The Rescue Medication tab will be available to patients 24 hours per day; tapping this tab will automatically display all required information for the patient to complete. The e-diary main menu will have
	

Original text with changes shown	New wording	Reason/Justification for change

will be used to record the following information:
 
 • WPI and SS scale • Mini-International Neuropsychiatric Interview (MINI) • FIQR • PGI-C • PROMIS 12a Physical Function • PROMIS Fatigue 8a • POMS • EQ-5D-5L • C-SSRS (Baseline and Since Last Visit) • IMD 
The tablet will be completed per the Study Procedures and Assessments (Table 1). The tablet main menu will contain individual tabs for each of the visits. Assessments will be completed by study site staff and/or the patient at the study site in the same order. Patients will be trained by the site staff on the use of the tablet at Visits 1 and 2, and at each visit throughout the study. Additional information on the tablet can be found in the Study Manual.
	
tabs for each of the aforementioned reports, on which the patient will tap to access the respective report. In the case of a missed report, the respective report will have “Missed” as an indicator to the patient on the main menu. Patients will be trained by the site staff on the use of the e-diary at Visits 1 and 2, and at each visit throughout the study. Additional information on the e-diary can be found in the Study Manual.
 
Tablet
 
The tablet will be dispensed to each clinical site. Patients will use the tablet at their visits to complete the required assessments. The tablet will be used to record the following information:
 
 • WPI and SS scale • Mini-International Neuropsychiatric Interview (MINI) • FIQR • PGI-C • PROMIS 12a Physical Function • PROMIS Fatigue 8a • POMS • EQ-5D-5L • C-SSRS (Baseline and Since Last Visit) • IMD 
The tablet will be completed per the Study Procedures and Assessments (Table 1). The tablet main menu will contain individual tabs for each of the visits. Assessments will be completed by study site staff and/or the patient at the study site in the same order. Patients will be trained by the site staff on the use of the tablet at Visits 1 and 2, and at each visit throughout the study. Additional information on the tablet can be found in the Study Manual.
	

Original text with changes shown	New wording	Reason/Justification for change
Section 4.1 Patient Inclusion Criteria (Other sections affected by this change: Section 5.8.1)		
a. approved for study participation by the Fibromyalgia Eligibility Review Committee (Section 5.8.1)	a. approved for study participation by the Fibromyalgia Eligibility Review Committee (Section 5.8.1)	This inclusion criterion was added to indicate there will be an independent review of patient enrollment eligibility.
Section 4.2 Patient Exclusion Criteria (Other sections affected by this change: Section 5.7, Appendix O)		
a. unable or unwilling to discontinue/washout of prohibited medications (Appendix J); selective serotonin reuptake inhibitors (SSRIs; with the exception of <60 mg/day of fluoxetine) or over-the-counter (OTC) medications used to treat depression or anxiety (Appendix J) are permitted if started at least 90 days prior to screening, have been on a stable dose for at least 6 90 days, and are expected to remain on a stable dose throughout the study, except for ≥60 mg of fluoxetine	a. unable or unwilling to discontinue/washout of prohibited medications (Appendix J); selective serotonin reuptake inhibitors (SSRIs; with the exception of <60 mg/day of fluoxetine) or over-the-counter (OTC) medications used to treat depression or anxiety (Appendix J) are permitted if started at least 90 days prior to screening, have been on a stable dose for at least 90 days, and are expected to remain on a stable dose throughout the study	This change was made to align the number of days since starting a depression/anxiety medication with the number of days for which the drug dose should be stable.
Section 5.1 Investigational Medicinal Products Used in the Study		
Investigational medicinal product is defined as the test IMP and matching placebo IMP to the test IMP. Patients will receive the IMP at Visits 3, 4, 5, and 6. Patients randomized to the 225 mg dose level will receive 1 injection of 225 mg fremanezumab and 2 injections of placebo; patients randomized to the 675 mg dose level will receive 3 injections of 225 mg fremanezumab; and patients randomized to placebo will receive 3 injections of placebo at each visit.	Investigational medicinal product is defined as the test IMP and matching placebo IMP to the test IMP. Patients will receive the IMP at Visits 3, 4, 5, and 6. Patients randomized to the 225 mg dose level will receive 1 injection of 225 mg fremanezumab and 2 injections of placebo; patients randomized to the 675 mg dose level will receive 3 injections of 225 mg fremanezumab; and patients randomized to placebo will receive 3 injections of placebo at each visit.	This change was made to specify the administration of IMP.
Section 5.11 Total Blood Volume (Other sections affected by this change: Appendix K)		
The total blood volume that will be collected for each patient enrolling in this study for scheduled evaluation of ADAs, fremanezumab concentrations, clinical laboratory tests, and biomarkers is approximately 195 248.5 mL for scheduled tests.	The total blood volume that will be collected for each patient enrolling in this study for scheduled evaluation of ADAs, fremanezumab concentrations, clinical laboratory tests, and biomarkers is approximately 248.5 mL for scheduled tests.	

Original text with changes shown	New wording	Reason/Justification for change
Section 6.1.1 Pain Intensity-Numerical Rating Scale		

The PI-NRS will be used to collect average daily pain intensity over the past 24 hours, the worst pain intensity over the past 24 hours, and at-the-moment pain intensity just prior to the use of rescue medication.
	
The PI-NRS will be used to collect average daily pain intensity over the past 24 hours, the worst pain intensity over the past 24 hours, and at-the-moment pain intensity just prior to the use of rescue medication.
	
This change was made to clarify how pain scores will be collected.

Section 6.1.8 Inventory of Medical Diagnoses (Other sections affected by this change: Sections 2.2, 3.5, 3.6.2, 9.6.3, 9.6.4.5, and Appendix B)		
